## OBJECTIVES:

1. To compare molecular response rates with the FND regimen followed by rituximab (chimeric anti-CD20 antibody) and interferon versus FND plus rituximab concurrently, followed by interferon, for patients with stage IV indolent lymphoma.
2. To compare the toxicity of these two regimens, including their effects on B- and T- cell subsets, immunoglobulins, and patterns of infections.
3. To compare failure-free and overall survival rates with these two regimens.
4. To identify and treat with a separate strategy those follicular lymphoma patients without bcl-2 mbr or mcr gene rearrangement ("germline" patients) because of their adverse outcome with FND alone in our prior experience.

## RATIONALE: (Be as concise as possible)

For all stage IV indolent lymphomas (with one exception; see Appendix B), the FND regimen appears to be comparable to the more intensive ATT regimen, in terms of remission rates, failure-free survival, and even molecular remission rates. The anti-CD20 monoclonal antibody rituximab is a promising agent with modest toxicities, none of which should overlap with the toxicities of FND. Hence, we propose to combine FND + rituximab, either concurrently or with rituximab as post-FND adjuvant therapy.

## ELIGIBILITY: (List Major Criteria)

- Previously untreated stage IV indolent B-cell lymphoma [Amendment May 2001: eligibility restricted to follicular lymphoma]
- Age <76

**TREATMENT PLAN:**

I. FND				
Fludarabine	25 mg/m 	IV	qd x 3 d1-3	(d2-4 in conjunction with IDEC)
Novantrone	10 mg/m 	IV	day 1 only	(day 2 only in conjunction with IDEC)
Decadron	20 mg	IV	qd x 5	d1-5
II. Rituximab 375 mg/m^2 per dose				
Dosing and schedule integrated with FND (see Section 5.3) or after FND (see section 5.2.3)				
III. Interferon alfa-2b maintenance 3 x 10^6 U/m^2/d x 14 days 1-14 of each 28 day maintenance cycle for 12 cycles, with decadron 8 mg qd x 3, days 1-3. (see Section 5.7.3 for integration of IFN cycles with rituximab)				

**STATISTICAL CONSIDERATIONS:**

The average yearly accrual rate for the current stage IV trial has been 33 patients per year. About 75% of patients can be expected to have a positive PCR. It will take 64 PCR positive patients in each arm to detect a difference of 25% in the twelve month molecular CR rate, assuming that the higher response rate was 85%. This assumes a two-sided alpha level of 0.05 and a power of 0.90.

Allowing for some inevaluable cases, approximately 210 patients will be accrued, which will probably take a little over 5 years.

**PATIENT EVALUATION: (Pretreatment and Interim Testing)**

	PRE STUDY	WEEKLY	EVERY 2 COURSES	EVERY 3 COURSES	EVERY 6 MONTHS	POST-THERAPY
H&P	X		X			q 3-6 mo
PS	X					
CBC	X	X				q 3-6 mo
U/A	X					
CXR	X					q 3-6 mo †
SMA 12, K, Mg*	X		X			q 3-6 mo
B2M	X			X		q 3-6 mo
BX/FNA*	X					
BM BX	X			X		q 6 mo †
LAG, CTs	X			X		q 6 mo †
PB markers, Ig's	X			X***		
PB PCR	X				X**	
BM PCR	X				X**	
ECHO or MUGA	X					

♣ K, Mg, etc as indicated, mainly for pts on ATT (see App. B)  
 \* when accessible; for phenotype, gene rearrangement  
 \*\* PCR for bcl-2 q 6 mo yr 1-3, q 12 mo thereafter. Contingency for PCR monitoring at 9 and/or 15 months for selected patients (see 7.2).  
 \*\*\* PB markers, Ig's: until recovery to normal  
 † Restaging off therapy (see section 7.7): at least q 6 mo until relapse or through year 5; then at least yearly

**MISCELLANEOUS INFORMATION: (Include any other information that you feel is pertinent to the study) (Three lines not to exceed 75 characters per line)**

- PCP prophylaxis: TMP/SMX, 2 DS tabs PO twice weekly (q Sat & Sun). For allergy, see section 5.4.3.2
- If PCP pneumonia occurs, subsequent chemotherapy cycles will be given without dexamethasone.

ESTIMATED ACCRUAL:

It is estimated that accrual will be   2   participants per month.

SITE OF STUDY: (please circle the appropriate answer)

This protocol is performed on an:

       INPATIENT              X   OUTPATIENT                   BOTH basis

LENGTH OF STAY: (What is the length and frequency of hospitalization)

RETURN VISITS: (How often must participants come to MDACC)

HOME CARE: (specify what (if any) treatment may be given at home)

WHERE THE STUDY WILL BE CONDUCTED:

- A)  ONLY AT MDACC      B)  MDACC + COMMUNITY PROGRAMS (CCOP, NETWORK)      C)  INDEPENDENT MULTICENTER ARRANGEMENTS

NAME OF SPONSOR/FUNDING SOURCE:

COMPETING PROTOCOLS: (Protocol number(s))

NONE

NAME OF RESEARCH NURSE/DATA MANAGER RESPONSIBLE FOR PROTOCOL:

SUBMIT PROTOCOL TO CLINICAL RESEARCH CENTER REVIEW COMMITTEE:

YES

NO

IF YOUR PROTOCOL HAS A DIAGNOSTIC STEP REQUIRING INFORMED CONSENT AND REGISTRATION ON THE PROTOCOL (E.G., A BLOOD TEST OR BIOPSY) THAT WILL DETERMINE WHETHER OR NOT THE PATIENT WILL SUBSEQUENTLY RECEIVED OR NOT RECEIVED EXPERIMENTAL THERAPY. PLEASE CHECK THE APPROPRIATE BOX(ES) SO THAT THE APPROPRIATE FIELDS MAY BE ESTABLISHED IN PDMS:

BLOOD TEST: YES	NO	BIOPSY: YES	NO	OTHER: YES	NO

## 1.0 OBJECTIVES

- 1.1 To compare molecular response rates with the FND regimen followed by rituximab (chimeric anti-CD20 antibody) and interferon versus FND plus rituximab concurrently, followed by interferon, for patients with stage IV indolent lymphoma.
- 1.2 To compare the toxicity of these two regimens, including their effects on B- and T-cell subsets, immunoglobulins, and patterns of infections.
- 1.3 To compare failure-free and overall survival rates with these two regimens.
- 1.4 To identify and treat with a separate strategy those follicular lymphoma patients without bcl-2 mbr or mcr gene rearrangement ("germline" patients) because of their adverse outcome with FND alone in our prior experience.

## 2.0 BACKGROUND

### 2.1 The Disease

The indolent lymphomas are characterized by a slow pace, typically by responsiveness to at least the initial therapy, but by inevitable relapse following standard therapy.

The histologic categories that comprise the majority of cases of indolent lymphoma are small lymphocytic lymphoma (SL), follicular small cleaved (FSC), and follicular mixed (FM) lymphoma as defined in the Working Formulation. However, it is notable that the recent Revised European American Lymphoma (REAL) scheme has: (a) created a scheme that more precisely categorizes several subsets of SL, including mantle cell lymphoma (MCL) which is considered not indolent; (b) challenged the concept that follicular large cell lymphoma (FLC) is intermediate grade and classifies FLC (follicle center lymphoma, follicular, grade III) along with the other follicular lymphomas.

Concerning subsets that have previously been categorized as SL: (a) we currently have a separate treatment strategy for MCL; (b) MALT lymphomas, when they present with localized disease, have a separate appropriate treatment strategy; but (c) when the marginal cell lymphomas present with disseminated disease, they are just as relentless as other advanced stage indolent lymphomas and therefore deserve, in our opinion, the same treatment strategy as other advanced stage indolent lymphomas.

Concerning FLC, inter-institutional and inter-pathologist differences in classification are well known for subclassification of follicular lymphomas. At MDACC, the distinction between follicular large non-cleaved versus cleaved lymphoma has been emphasized in recent years, the latter being considered indolent and thus eligible for this protocol, while the former is considered aggressive and such cases are triaged to other protocols. It is acknowledged that the distinction among precise cell types among the follicular lymphomas is at times arbitrary. Pertinent to therapy considerations (see below), FLC is unique among the intermediate grade lymphomas in that responsiveness to fludarabine is typically good.

An important hallmark of the follicular lymphomas is the t(14;18) translocation which results in bcl-2 gene rearrangement in the majority of cases. Among other things, this breakpoint provides a marker that can be followed by PCR (see below). There is beginning to be evidence that the specific breakpoint site (mbr; mcr) may be prognostically important, and the "germline" (i.e., not mbr or mcr rearranged) cases may do poorly with FND chemotherapy. Accordingly, in this protocol such patients are assigned to a separate treatment strategy

## 2.2 Chemotherapy Approaches

Using therapy based on alkylating agents such as cyclophosphamide and chlorambucil, depressingly little has changed in survival outcomes in the past 30 years. In the intermediate grade lymphomas, the impact of doxorubicin is compelling; but the impact of the addition of doxorubicin in indolent lymphoma is arguable. To date, the impact of interferon (IFN) appears mainly on duration of remission rather than on survival. The purine nucleoside analogs, especially fludarabine, are a new class of drugs that have appeared very promising in indolent lymphoma and chronic lymphocytic leukemia. Fludarabine has been used extensively in relapsed indolent lymphoma, both singly and in combination regimens. At MDACC, the FND regimen has been used successfully in front-line therapy, with early results showing it to be comparable to the more intensive "ATT" regimen. One subset of follicular lymphoma for whom FND may be inferior to ATT are those with "germline" status for bcl-2.

## 2.3 PCR for bcl-2

The initial description of the utility of PCR for bcl-2 in detecting the subclinical presence of rearranged cells was here at MDACC. Since then, the role of this assay as a surrogate endpoint and marker of treatment success has generated worldwide interest.

The attainment of PCR-negativity with any therapy approach except bone marrow transplantation has been difficult. In recent years, reversion to PCR-negativity has been accomplished with our "ATT" regimen. Thus, it is possible to explore whether attaining PCR-negativity is a desirable goal that correlates with more durable remission, as has been observed with bone marrow transplantation and *ex vivo* purging. Our preliminary results indicate that PCR-negativity does indeed correlate with longer remission following conventional dose chemotherapy.

Our recent experience (DM 92-103) with FND has shown that this regimen, too, can induce PCR-negativity. The current protocol is a logical extension of that experience.

## 2.4 Anti-CD20 Monoclonal Antibody Therapy (rituximab)

Monoclonal antibodies are of tremendous theoretical appeal as therapeutic agents. Our understanding of the expression of surface antigens in B-cell malignancies has led to numerous trials of monoclonal antibodies in B-cell malignancies. Stumbling blocks have been encountered, including the immunogenicity of rodent monoclonal antibodies and the myelosuppressive effects of radioimmunoconjugates.

A chimeric anti-CD20 antibody, rituximab, has emerged as a promising single agent. Since it is predominantly a human protein, host immune responses against the agent have been infrequent. Since it is not conjugated to a toxin or isotope, its spectrum of toxicity is relatively modest. And, most importantly, as a single agent

is has been shown to have promising activity in patients with relapsed B-cell lymphoma.

Rituximab has been used in conjunction with standard CHOP chemotherapy, with promising early results. Other combination trials, including the current protocol, are planned.

The most extensive experience with rituximab, as a single agent, has utilized a schedule of weekly dosing for four weeks. Its relative lack of immunogenicity suggests that re-treatment or longer-term treatment schedules are feasible. This issue is to be explored in one arm of the current trial.

The experience with rituximab in conjunction with CHOP chemotherapy utilized a total of six doses of the antibody, integrated into the chemotherapy cycles in a fashion similar to the other proposed arm of our current protocol. This integration of rituximab with chemotherapy has already been shown feasible and effective with CHOP. The current protocol will be the initial experience of the integration of rituximab with the FND regimen.

Rituximab appears to be capable of effecting reversion of PCR for bcl-2 in the peripheral blood and bone marrow from positive to negative. Using the antibody alone, the peripheral blood became PCR-negative in 68% and the bone marrow in 50%. In conjunction with CHOP, the peripheral blood became PCR-negative in almost 80%. Since CHOP alone appears to result in PCR-negativity only infrequently, the expectation of higher rates of PCR negativity, coupled with *in vitro* evidence of synergism between rituximab and some chemotherapeutic agents, warrants further experience with concurrent antibody plus chemotherapy.

Given the potential of rituximab to produce, as a single agent, PCR negativity in the blood and marrow, and since some chemotherapy-treated patients do not achieve PCR negativity, the adjuvant use of the antibody may result in higher molecular remission rates (although at a later time point than 12 months). This potential for eradication of minimal residual disease, and extrapolation from our previous favorable experience with adjuvant interferon, provide the rationale for the adjuvant antibody strategy.

As previously discussed, a small subset of patients with follicular lymphoma are germline for bcl-2, and our experience suggests that these patients may be prognostically unfavorable, in that an intensive regimen such as ATT appears necessary for best results. For these patients, we propose integration of rituximab with ATT.

### 3.0 BACKGROUND DRUG INFORMATION

3.1 For fludarabine, mitoxantrone, dexamethasone, interferon alfa-2b (Intron A), and the agents in the CHOD-Bleo/ESHAP/NOPP program, data available on request [contact]).

3.2 Rituximab chimeric anti-CD20 antibody.

### 3.2.1 Investigational Drug Nomenclature

- IDEC Pharmaceuticals code designation: IDEC-C2B8 (IDEC-102)
- Generic name: Rituximab
- CAS Registry number: 174722-31-7
- IND number: BB-IND 4904

### 3.2.2 Origin of the IDEC-C2B8 cell line.

The chimeric mouse/human anti-CD20 monoclonal antibody, rituximab (IDEC-C2B8 [IDEC-102]), is a human gamma 1 kappa antibody with mouse variable regions isolated from a murine anti-CD20 monoclonal antibody (2B8). This chimeric antibody, which is secreted by the Chinese hamster ovary (CHO) transfectoma clone 8-8F12-5E5-50C9, binds with high affinity to CD20-positive cells, performs human effector functions in *in vitro* assays, and specifically depletes B cells *in vivo*. The CHO transfectoma was produced by inserting DNA coding for the chimeric immunoglobulin chains into the CHO cell line DG44 by electroporation, and selecting for a clone resistant to G418 (Genetecin) that secreted chimeric immunoglobulin (Clone 8-8F12). Subsequently, the immunoglobulin production was enhanced through selection of a clone resistant to 5 nM methotrexate (MTX) (clone 8-8F12-5E5); Phase I and Phase II material was produced using this clone. Immunoglobulin production was further enhanced through selection of a clone resistant to 50nM MTX (clone 8-8F12-5E5-50C9). Material produced from this clone has been used in a Phase II combination study with CHOP.

3.2.2.1 Development Code: IDEC-C2B8 (IDEC-102)

3.2.2.2 Other Designations: Mouse/human chimeric monoclonal antibody for CD20 antigen; anti-CD20 antibody, chimeric pan-B.

### 3.2.3 Clinical Formulation

Clinical supplies for this study will be manufactured by either IDEC Pharmaceuticals in San Diego, CA or Genentech Incorporated in South San Francisco, CA.

Rituximab from either source will be provided to the clinical sites packaged in single use 10 mL (100 mg) and 50mL (500 mg) Type I glass vials at a concentration of 10 mg of protein per mL. The product is formulated in 7.35 mg/mL sodium citrate buffer, containing 7 mg/mL polysorbate 80, 9.0 mg/mL sodium chloride and Sterile Water for Injection. The pH is adjusted to 6.5.

Rituximab may be produced by the mammalian (Chinese Hamster Ovary) cell suspension culture in a nutrient medium containing 100 mg/mL of the antibiotic gentamicin. The antibiotic is not detectable in the final product.

### 3.2.4 Storage

Rituximab for clinical use should be stored in a secure refrigerator at 2-8° C.

### 3.2.5 Reconstitution and Dilution of rituximab

Using a sterile syringe and a 21 gauge or larger needle, transfer the necessary amount of rituximab from the vial into a partially filled IV pack containing sterile, pyrogen-free 0.9% Sodium Chloride, USP (saline solution). The final concentration of Rituximab should be approximately 1 mg/mL. Mix by inverting the bag gently.

For lots 0122-0125 the final preparation should be administered through a 0.22 micron low-protein binding in line filter, such as IMED 9216, into the outflow port of the bag containing the infusion solution. For other lots this will not be required.

Caution should be taken during the preparation of the drug. (See Appendix I). Parenteral drug products should be inspected visually for particulate matter prior to administration. Preparations of rituximab containing visible particles should not be used. As with all parenteral drug products, aseptic procedures should be used during the preparation and administration of rituximab.

NOTE: DO NOT USE A VACUUM APPARATUS to transfer rituximab from the syringe to the infusion pack. DO NOT USE evacuated glass container which require vented administration sets, because this causes foaming when air bubbles pass through the solution.

### 3.2.6 Product Administration

In calculating body surface area, actual height and weight should be used, that is, there will be no downward adjustment to "ideal" weight. Dosage calculations for all treatments will be calculated using the patient's body surface area as determined during the screening evaluation. The dose level of rituximab will not be adjusted.

### 3.2.7 Pre-Clinical Experience

Rituximab (IDEC-102) is a chimeric IgG1 kappa monoclonal antibody, with mouse variable and human constant regions, that recognizes the CD20 antigen expressed on normal B cells and most malignant B-cell lymphomas. The antigen, important in cell cycle initiation and differentiation, is expressed strongly in over 90% of B-cell lymphomas. Rituximab shows specificity for the CD20 antigen and binds with an apparent affinity of  $5.2 \times 10^{-9}$ M.

*In vitro* mechanism of action studies have demonstrated that this antibody binds human complement and lyses lymphoid B cell lines. It has significant activity in assays for antibody-dependent cellular cytotoxicity (ADCC). High dose safety studies in cynomolgus monkeys revealed a decrease in platelet levels between 7 and 33% at the two higher doses on day 1 with recovery between days 7 and 14. A reduction in white blood cells between 13 and 31% was seen in 5 of 6 monkeys studied with recovery beginning by day 8. In 4 of 6 monkeys at 12 to 34% decrease in segmented neutrophils was observed; recovery occurred by day 14 in one animal. Hematologic changes were not dose-dependent. In this study and during other rituximab testing in cynomolgus monkeys, vomiting

was noted in a minority of monkeys. Dose levels of 20 mg/kg weekly for up to eight weeks showed no significant adverse reactions, toxicological events or any abnormal histopathology. The biologic effect of four weekly doses of rituximab in cynomolgus monkeys resulted in B-cell depletion in peripheral blood (PB), lymph nodes (LN) and bone marrow (BM). Three weeks after 4 weekly doses there was a >75% decrease of B cells in the bone marrow. Recovery of the B cells in the peripheral blood (to >75% of baseline) usually occurred within 60 days following the last dose.

### 3.2.8 Clinical Experience

Previous clinical trials have shown that outpatient therapy with rituximab, completed within 22 days, is safe and effective in the treatment of patients with relapsed low-grade/follicular non-Hodgkin's lymphoma.

#### Phase I/II Trials

Two previous Phase I/II dose-escalation studies of rituximab were conducted (IDEC Protocols 102-01 and 102-02) in patients with relapsed or recurrent non-Hodgkin's lymphoma [Maloney, 1994#1537;3]. Fifteen patients were enrolled in a single-dose study (IDEC 102-01), (10 to 500 mg/m^2 of rituximab) and 47 patients in a multiple-dose study (IDEC 102-02) (125, 250, or 375 mg/m^2 once weekly times four). Clinical activity was noted in seven of 15 patients in the single-dose trial with two partial responses lasting 8.1 and 8.5 months, and five minor responses lasting between 0.9 and 6 months. In the multiple-dose study, three complete responses and 14 partial responses were noted in 34 evaluable patients (375 mg/m^2 rituximab) with a median response duration of 8.6 months. Median time to progression (TTP) in responders was 10.2 months; TTP exceeded 20 months in five patients, two of whom have ongoing responses of 30+ months. No correlation between pharmacokinetic parameters clinical response was apparent in the single-dose study; however, a positive correlation was observed between clinical response and antibody serum levels prior to the second infusion in the multiple-dose study.

Overall, adverse experience were mostly Grades 1 and 2 and consisted primarily of infusion-related events (fever, asthenia, chills, headache, and less commonly, bronchospasm, hypotension and agioedema[subjective sensation of tongue and throat swelling]). Hematologic toxicity was usually mild and reversible. In both trials, a rapid and selective depletion of circulating B-cells was observed following treatment. In the Phase I/II study, mean serum immunoglobulin levels remained stable, although some patients experienced transient reductions of IgOs. In both studies, it was concluded that intravenous infusions of rituximab appeared safe and well tolerated and demonstrated significant activity in patients with relapsed B-cell lymphoma.

#### Phase III Open-Label Trial

A Phase III multicenter trial completed patient entry in March 1996 with a total enrollment of 166 patients [4]. Treatment consisted of weekly x four infusions at 375 mg/m^2. Analysis revealed that adverse events (AE) were primarily related to first infusion and consisted of fever, chills, nausea, and headache. There was a marked reduction in the incidence of AEs in

subsequent infusions. Overall, 6% of all events (72 of 1163) observed during study treatment and follow-up were Grade 3 and 4, and of those, 3% (39 of 1163) were related to study treatment. There were no incidences of human antichimeric antibody (HACA) during this trial. (The overall incidence of HACA in over 300 patients participating in all rituximab trials has been <1% and HACA was not clinically significant in those in whom it occurred).

Ninety-one percent of patients (151 of 166) were evaluable for efficacy and achieved an overall response rate of 50% with 6% CR and 44% of PR. The onset of response was as early as even weeks and responses were seen in patients with bulky and extranodal disease. CT scans of responders were reviewed and confirmed (blinded audit) by an independent panel of lymphoma experts following established response criteria. Median time to progression for responders had not been reached with 9+ months median follow-up.

## 4.0 ELIGIBILITY

- 4.1 Previously untreated patients, younger than 76 years old, with stage IV follicular lymphoma (including follicular large cleaved cell) or small lymphocytic lymphoma. [Amendment May 2001: Eligibility for last 25-30 patients restricted to follicular lymphoma (see section 10.2)]
- 4.1.1 Patients with chronic lymphocytic leukemia (absolute lymphocyte count >5000  $\mu$ L) are excluded.
- 4.1.2 Patients with divergent histologies (intermediate grade in one site and low grade in another) will not be eligible.
- 4.1.3 It is known that there can be a continuum of histologies, spanning elements of indolent and aggressive. While patients with truly divergent histologies are specifically excluded (see 4.1.2), other variants can be eligible, as follows:
- F + DSC\* - eligible.
  - F + DM\* - eligible.
  - Sclerosing SCCL or mixed cell - eligible (even if follicular architecture not definite)
  - Follicular large noncleaved cell -- the distinction between this entity and follicular large cleaved can be arbitrary and is of debatable significance. But it has been our practice to treat follicular large noncleaved as an intermediate grade lymphoma. Hence, if eligible, such patients should be treated on the appropriate intermediate grade protocol. However, both FND and rituximab have established efficacy in FLCL (without regard to cleaved or not), so if a patient is not eligible for an intermediate grade protocol (e.g., because of SCCL in the marrow), then registration on this trial is permitted.
  - FSC or FM with areas of FLC – eligible.
  - FSC or FM with areas of DLC – not eligible unless reviewed with P.I. and an addendum on the pathology report is issued stating that the disease is best categorized as an indolent lymphoma.

\*- in F & D cases, any extent of follicular architecture is traditionally accepted, but in cases that are > 75% diffuse, please review with P.I. and Pathology as for 4.1.3 (f) above.

4.2 Patients must sign an informed consent indicating that they are aware of the invitational nature of the study, in keeping with the policies of the hospital.

4.3 Ineligible patients are:

4.3.1 Patients who are unable or unlikely to be able to adhere to the treatment plan or to return to Houston for follow-up visits because of geographical, economic, emotional, or social considerations are not eligible for this study.

4.3.2 Patients with an absolute peripheral granulocyte count of < 1,000 and platelet count < 100,000 unless due to marrow infiltration or hypersplenism.

4.3.3 Patients with hepatic dysfunction, defined as bilirubin of > 1.5 mg%, unless the alteration is due to lymphoma.

4.3.4 Patients with a serum creatinine level >1.5 mg% unless the alteration is due to lymphoma.

4.3.5 Patients with HIV infection should not be registered on this protocol.

4.3.6 Pts with an antecedent malignancy whose prognosis is poor (< 90% probability of surviving for 5 yrs).

4.3.7 All patients should have a cardiac ejection fraction of  $\geq 50\%$  by echocardiography or MUGA. If a patient without cardiac symptoms has an aberrant low LVEF (< 50%), please consult cardiology and discuss with P.I.

4.3.8 Patients who will not accept transfusions of blood products or supportive care measures such as antibiotics are not eligible for this study.

4.3.9 Female patients must not be pregnant or lactating, and men and women of reproductive potential must follow accepted birth control methods.

4.4 Additional safety guidelines for use of interferon (see Appendix F): These considerations are not exclusions to eligibility since:

- (1) Some abnormalities might change before IFN maintenance, e.g., organ dysfunction related to disease might likely improve with treatment; or
- (2) some guidelines, e.g., a history of depression, might mitigate against IFN but would not exclude the patient's being treated on protocol with all the other elements of the program.

Please discuss any concerns about IFN with the P.I.

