## 5.0 TREATMENT PLAN

5.1. All patients must be registered with Data Management at [name]. They will be interviewed first by the Research Nurse before registration.

5.1.1 Follicular lymphoma patients who are known not to have bcl-2 gene rearrangement will not be randomized -- they will proceed directly to therapy with the ATT regimen (see Appendix B).

If there is no threatening disease and the clinician judges that it is safe to wait for the bcl-2 data, the initiation of therapy may be delayed (This is encouraged.)

However, if therapy is needed, it will not be delayed just for the bcl-2 report. If bcl-2 status is not known or pending, patients will be randomized. If, after therapy with FND begins, a patient is found to be germline for bcl-2, the patient will be crossed over to ATT (see strategy outline in Appendix B).

5.1.2 Randomization will be stratified for: tumor mass size < 5 cm vs. ≥ 5 cm; age < 60; FLC histology; SL histology; and suitability for the watch-and-wait policy followed at other institutions.

5.2 ARM 1 (delayed anti-CD20 arm) will consist of consecutive courses of Fludarabine/Mitoxantrone/Dexamethasone (FND), followed by rituximab.

Agent	Dose	Days	Route	Time	Total Dose
Fludarabine	25 mg/m 	1-3	IV	15 min	75 mg/m 
Mitoxantrone	10 mg/m 	1	IV	15 min	10 mg/m 
Decadron	20 mg	1-5	IV or PO	15 min	100 mg

5.2.1 Duration of therapy and intervals between courses:

- a) The courses should be repeated every 28 days according to recovery from myelosuppression.
- b) The total length of treatment will be 8 courses unless cumulative myelosuppression is encountered, in which case the treatment will be finished after 6 courses. Cumulative myelosuppression is defined as recovery of granulocytes to ≥ 1,000 or platelets to >100,000 requiring more than 6 weeks.

5.2.2 Patients older than 60 years will receive full doses of chemotherapy. Anyone experiencing delayed recovery of granulocyte counts (>35 days) or neutropenic fever will be candidates for G-CSF (Neupogen), with the chemotherapy doses adjusted down one dose level. The G-CSF dose will consist of 300 mcg total dose daily, subcutaneously. The dose can be increased to 480 mcg daily at the clinician's discretion.

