### 5.6.2 For All Other Toxicities (see Appendix D)

Grade 0-2	No Change
3	Decrease one level
4	Stop Treatment

5.6.3 All courses will be held pending hematologic recovery to granulocytes >1,000 and platelets >100,000, and non-hematologic toxicities to grade <1.

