#### IV. Recommended Dose Modification Guidelines

1. For Hematologic Toxicity -- see Section 5.6
2. For Renal Toxicity

Serum Creatinine (mg%)		Creatinine Clearance (cc/min)	Modification of Cisplatin
0.6 - 1.4	or	> 75	None
1.5 - 2.0	or	60 - 74	33% reduction
2.1 - 2.5	or	40 - 59	50% reduction
>2.5 - 4.0	or	<39	Delete*

\* Cisplatin could be given at 25% dose, after consultation with Study Chairman, if renal failure is secondary to lymphoma.

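### Section 4.3.2 excludes only patients with both counts low, where *or* is needed; a lesser gap is that the between-course rules ignore the cause of low counts in patients admitted under its exception

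*Combined protocol and SAP*

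**What the plan says.** Section 4.3 lists the ineligible patients. Item 4.3.2 reads: "Patients with an absolute peripheral granulocyte count of < 1,000 and platelet count < 100,000 unless due to marrow infiltration or hypersplenism". The eligibility summary at the front of the protocol has no count criterion.

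Three treatment rules use the same or nearly the same limits:

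- Section 5.6.3, under the dose modification guidelines: "All courses will be held pending hematologic recovery to granulocytes >1,000 and platelets >100,000".
- Section 5.2.1(b): "Cumulative myelosuppression is defined as recovery of granulocytes to ≥ 1,000 or platelets to >100,000 requiring more than 6 weeks". The consequence, against a plan of 8 courses, is given just before: "in which case the treatment will be finished after 6 courses".
- Section 5.2.2: "Anyone experiencing delayed recovery of granulocyte counts (>35 days) or neutropenic fever will be candidates for G-CSF", with chemotherapy lowered by one dose level.

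Section 5.3 refers Arm 2 to the same interval, G-CSF and course-omission rules. None of the three rules mentions the cause of a low count or its value at entry.

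**The concern.** The main issue is the connective in 4.3.2. As written, one severely low count from any cause does not exclude a patient if the other count is adequate. FND is myelosuppressive, and 5.6.3 treats either low count as reason enough to wait. An entry criterion looser than the re-treatment criterion, for a count not explained by lymphoma, is hard to defend on safety grounds and does not look intended.

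The secondary issue concerns patients admitted on purpose under the exception for marrow infiltration or hypersplenism. Between courses they are held to a level they may not have had at entry. If recovery takes more than six weeks, they meet the definition of cumulative myelosuppression even where the disease, and not the drug, is the reason.

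**Working it through.** The plan gives no figure on this point to reproduce. The check is a comparison of rules, followed by simple dose arithmetic.

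**1. Entry criterion against hold rule, for counts not due to lymphoma**

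| Granulocytes | Platelets | Excluded by 4.3.2 (*and*) | Excluded if *or* | Fails 5.6.3 limits |
|---|---|---|---|---|
| low | low | yes | yes | yes |
| low | adequate | no | yes | yes |
| adequate | low | no | yes | yes |
| adequate | adequate | no | no | no |

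The two middle rows are the gap. Granulocytes of 300 with platelets of 150,000 fall in the second row. With *or*, the excluded set equals the set that fails 5.6.3, apart from counts exactly at 1,000 or 100,000, which 4.3.2 admits and 5.6.3 does not pass. Section 5.2.1(b) also joins the two counts with *or*.

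**2. Is there another check before course 1?** Section 5.6.3 is best read as starting with course 2 (see the objection). On that reading 4.3.2 is the only numeric minimum for granulocytes or platelets before the first FND course. The count limits in Appendix F concern interferon only.

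**3. Patients admitted under the exception.** Sections 5.6.3 and 5.2.1(b) have no clause for them, and neither do 5.2.2 and the dose table in 5.6.1. Appendix D offers a separate grading scale for marrow-infiltrative disease, but only where the protocol specifies it, and the protocol body does not.

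**4. Size for one affected patient, at dose level 0**

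- Fludarabine per course: 25 × 3 = 75 mg/m². Eight courses: 75 × 8 = 600. Six courses: 75 × 6 = 450. Ratio 450/600 = 0.75, so 25% less.
- Mitoxantrone: 10 × 8 = 80 mg/m² against 10 × 6 = 60. Ratio 60/80 = 0.75, so 25% less.
- Delay when a course is held past six weeks: 42 − 28 = 14 days or more, assuming that the weeks run from day 1 of the previous course.
- Rituximab in Arm 2 (5.3): 2 doses in course 1 plus 1 in each of courses 2–5 makes 6. Four of the 6 are tied to day 1 of courses 2–5, so a held course delays the antibody too. Omitting courses 7 and 8 removes none.

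**The case against.** **The *and* may be loose drafting.** An investigator would probably not start FND in a patient with unexplained granulocytes of 300. That limits how often the gap matters. It does not change what the criterion says, and no other section corrects it.

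**The two parts cannot both be harmful on one reading of 5.6.3.** If 5.6.3 governed course 1, the patient with granulocytes of 300 would be held, so the *and* would expose nobody to treatment at that count; it would only make eligible a patient who could not start. If 5.6.3 begins with course 2, the exposure is real. This is correct, and it is why the main point rests on the second reading.

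**A reader might infer that 5.6.3 blocks course 1 for patients admitted under the exception.** The text does not support this. The rule stands among the dose modification guidelines and speaks of recovery, which presupposes treatment already given. Section 5.2.1(a) likewise ties the repeating of courses to recovery from myelosuppression.

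**A reader might infer that the protocol handles the renal case properly and forgot the hematologic one.** Section 4.3.4 lists as ineligible "Patients with a serum creatinine level >1.5 mg% unless the alteration is due to lymphoma", and Appendix B has the note "Cisplatin could be given at 25% dose, after consultation with Study Chairman, if renal failure is secondary to lymphoma", next to a hematologic line that says only "For Hematologic Toxicity -- see Section 5.6". But cisplatin belongs to ATT, the regimen for germline patients, and not to randomized FND. Section 4.3.3 admits raised bilirubin due to lymphoma with no matching dosing clause. One footnote is not a pattern from which the hematologic rules depart.

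**There is room for judgment already.** Section 5.6 is headed as guidelines, and 5.3 describes the omission of courses 7 and 8 in the same way. The word cumulative suggests a drug effect that builds up. Section 5.2.2 offers G-CSF from 35 days, a week before the six-week limit, though with a dose reduction and no help for platelets. Section 11.3 makes the Study Chairman the final arbiter of disputed toxicity. This stands, and it reduces the secondary point to a clarification.

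**Conclusion.** The main point holds on the text: 4.3.2 as written lets in patients with a single severe cytopenia not due to lymphoma, which does not fit the limits in 5.6.3 and 5.2.1(b). This is a one-word eligibility error with a small safety consequence. The safety part assumes that 5.6.3 applies from course 2.

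The secondary point holds as a minor gap in the between-course rules. Its size for one patient is at most two courses (25% of planned FND) or a delay of 14 days or more. Six courses is itself a duration that the protocol allows. The rules are the same in both arms, and 9.1 removes minor responders after 4 courses, which limits the number exposed.

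The documents do not say how many patients enter with low counts of either kind, and no estimate is offered. A reader might infer bias in the 12-month molecular response or a loss of power; nothing in the documents shows either, and the 64 per arm is unaffected.

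**What to change.** 1. In 4.3.2 change *and* to *or*, and keep the exception for marrow infiltration and hypersplenism. Cost: one word, and a few patients with a single low count of other cause become ineligible.
2. In 5.6.3 state that the rule applies from course 2 on. Make this change together with the first: on its own it would confirm that nothing stops course 1 in a patient with one low count.
3. Add to 5.6.3 and 5.2.1(b) that, for patients admitted under the exception, the decision to hold a course, or to stop after 6, is made with the P.I. according to whether the low count is due to disease or drug. Cost: one clause in each place and some P.I. time. Entry counts are already collected under 6.2.

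Do not make the count before course 1 the threshold for re-treatment unless an absolute floor is set as well. Without one, an entry granulocyte count of 300 could become the level at which a myelosuppressive regimen is repeated.
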